4.2 TRIAL PERIODS, OBSERVATION AND ANALYSIS TIMES

Where durations are to be calculated (e.g. treatment duration), these will be derived based on the interval in days (end date – start date + 1) and converted to months and years if needed, using 30.4375 and 365.25, respectively, as denominator if not otherwise specified.

For the investigational medicinal product (IMP) exposure, treatments administered from the date of first randomized pirfenidone/placebo treatment up to the date of completion of double-blind treatment or date of early treatment discontinuation, will be regarded.

For drug safety, analyses will be restricted to AEs or assessments that occurred from the first day of randomized treatment until the date of last positive dose of randomized treatment plus 28 days.

Safety analyses for the 12-month follow-up period will be performed using the time window from the safety follow-up period start up to the study completion/discontinuation visit.

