4.2.1 Study Days

Study days will be defined as the number of days since randomization, and is calculated as:

- Study day = Assessment date randomization date + 1, for assessments on or after the randomization date.
- Study day = Assessment date randomization date, for assessments before the randomization date.

The day of randomization will be study day 1.

Pirfenidone — F. Hoffmann-La Roche Ltd

4.2.2 Baseline and Screening Observations

Table 1 Definition of Baseline and Screening Observations

| | Definition |
|----------------|---|
| Baseline data | Baseline is defined as the last valid assessment prior to first intake of randomized study drug (pirfenidone/placebo). |
| | This may not be the same as the Day 1 (Week 1) visit as per eCRF. In case that Day 1 (Week 1) visit data is missing and the randomized treatment is given, data from the screening period will be used as baseline. In addition, if randomized treatment is not given then baseline will be defined as the last valid assessment collected either screening or day 1. |
| | Generally, it is assumed that measurements referring to the Day 1 (Week 1) visit have been performed before randomized study drug (pirfenidone/placebo) was given. |
| | Adverse events occurring on the date of first randomized pirfenidone/placebo treatment will not be considered baseline, but treatment-emergent. |
| Screening data | Screening measurements are all the measurements performed before the randomization date. |

4.2.3 On-treatment Assessments for Efficacy Analyses (Double-blind Treatment Period)

For efficacy analyses, on-treatment assessments will be the assessments performed on or after the randomization date until the double-blind treatment completion or discontinuation date.

4.2.4 On-treatment Assessments for Safety Analyses (Double-blind Treatment Period)

For safety analyses, on-treatment assessments will be the assessments performed on or after the first dose of randomized pirfenidone/placebo date until the last positive dose of randomized treatment plus 28 days.

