4.2.5 On-treatment Assessments (12-Month Safety Follow-up Period)

Details of all data recorded during the 12-month safety follow-up period will be presented. This period starts on the day of the first positive dose of pirfenidone after the 28 days follow-up visit for patients who completed the double-blind treatment period without being discontinued the study. The safety follow-up period ends with the study completion/discontinuation visit, with a maximum duration of 12 months plus 28 days.

Pirfenidone — F. Hoffmann-La Roche Ltd

Safety follow-up analyses will be presented separately from double-blind treatment phase ones.

4.2.6 Cut-off points

The clinical cut-off for the primary analysis will occur when the last patient has completed the final safety Follow-up Visit, 28 days after the double-blind treatment period.

There will be a second cut-off for the final analysis when all patients have completed the 12-month safety follow-up period.

For each patient the total length of the trial is expected to be up to a maximum of 91 weeks. The trial duration includes the washout period of up to 4 weeks, the screening period of up to 3 weeks, the double-blind treatment period of 24 weeks, the follow-up period of 4 weeks, the open-label safety follow-up period up to 12 months (52 weeks) plus 28 days and a final safety Follow-up Visit 4 weeks after the last dose.

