4.6.2 Adverse Events

Verbatim descriptions of adverse events (AEs) will be mapped to a preferred term (PT) and system organ class (SOC) using the Medical Dictionary for Regulatory Agencies (MedDRA®). MedDRA version 20.1 or above and related SMQ lists will be used for coding.

AEs will be graded according to the National Cancer Institute Common Terminology Criteria for Adverse Events (NCI CTCAE), Version 4.03. For AEs of varying severity, the most severe grade as documented on the eCRF will be used in the summaries. An AE will be considered severe if the most extreme grade will be larger or equal to 3.

After informed consent has been obtained but prior to initiation of trial treatment, only serious adverse events caused by a protocol-mandated intervention (e.g. invasive procedures such as biopsies, discontinuation of medications) should be reported. All adverse events will be reported until 28 days after the last dose of study drug. After this period, the Investigator should report any SAEs that are believed to be related to prior study drug treatment.

For safety analysis of the double-blind treatment period treatment-emergent adverse events (TEAEs) will be defined as:

• AEs that started or worsened on or after first intake of randomized treatment until last positive dose of randomized treatment + 28 days

Adverse events that are reported after informed consent but before the first intake of randomized treatment will be considered as non-treatment-emergent AEs. These might include AEs that occur during the screening period.

Post-treatment AEs are not expected to occur, but will be defined as AEs that are reported more than 28 days after the last dose of randomized treatment for patients who do not enter the 12-month safety follow-up period. Those AEs will be listed.

Pirfenidone — F. Hoffmann-La Roche Ltd

The analysis of AEs within the framework of the primary study analysis will focus on treatment-emergent AEs (TEAE).

An overview of patient safety profile will present the number and proportion of patients in each treatment arm experiencing:

- Any and any related treatment-emergent adverse events (TEAE)
- Any and any related serious treatment-emergent adverse events (serious TEAE)
- Any and any related severe treatment-emergent adverse events (TEAEs ≥ Grade 3)
- Any and any related TEAE of special interest (AESI). Adverse events of special interest for this trial include the following:

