4.7 SAFETY FOLLOW-UP ANALYSES

Data collected during the safety- follow-up period will be analyzed in the following way.

Adverse events during the 12-month safety follow-up period for pirfenidone treatment will be defined as:

 AEs that started or worsened on or after the date of safety follow-up period start until the end of the safety follow-up.

Pirfenidone — F. Hoffmann-La Roche Ltd

The safety follow-up population will be used for these analyses.

Summary tables for the incidence of AEs, related AEs, serious AEs, related serious AEs, severe AEs and severe related AEs will be summarized by system organ class (SOC) and preferred term (PT). Frequencies and percentages of patients experiencing (at least) one event in the respective category will be presented by decreasing frequencies. If patients have more than one AE within a SOC or PT they will be counted only once for the respective SOC or PT. Additionally, the total numbers of AEs will be provided for each SOC and overall. As with the end of the double-blind treatment period, an overview of safety will also be presented.

Pirfenidone exposure during safety-follow-up will be analyzed in a similar fashion as described in Section 4.7.1 with regard to treatment duration and amount of drug intake.

Data of laboratory assessments (AST, ALT, bilirubin, and alkaline phosphatase) and vital signs during safety-follow-up period will be analyzed in a similar fashion as described in Section 4.7.4 and Section 4.7.5.

Data will be presented by randomized treatment labeled as 'Randomized Pirfenidone' and 'Randomized Placebo'.

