4.8 MISSING DATA

With exception of the tipping point analysis described in section 4.5.8, missing data will not be imputed. Other exceptions will be made for the data related to adverse events and concomitant medications as described below.

For adverse events, missing start dates will only be imputed for determination of whether the adverse event is considered to be treatment-emergent or not.

Incomplete or missing onset dates will be imputed to the earliest date possible (using any reliable portions of the onset date that are available). The onset day is considered unreliable if the month or year portions of the date are missing.

In case the month portion of the AE start date is missing, the AE start date will be imputed to the earliest day possible by using the following principles:

- If Treatment Start Date is missing, then the AE Start Date will be imputed as 01-01-YYYY or the earliest date regarding signature of informed consent, screening date or randomization date, whichever is the later one
- When the Treatment Start Date is not missing, and the years of AE Start Date and Treatment Start Date coincide, the AE onset date will be set to the Treatment Start Date
- When the Treatment Start Date is not missing, and the years of the AE Start
 Date and the Treatment Start Date do not coincide, then the AE Start Date will be
 imputed as 01-01-YYYY or the earliest date regarding signature of informed
 consent, screening date or randomization date, whichever is the later one

Pirfenidone — F. Hoffmann-La Roche Ltd

In case the day portion of the AE Start Date is missing, the AE Start Date will be imputed to the earliest day possible as follows:

- If the Treatment Start Date is missing, then the AE Start Date will be imputed as 01-MMM-YYYY or the earliest date regarding signature of informed consent, screening date or randomization date, whichever is the later one
- When the treatment date is not missing, and the years and months from the AE Start Date and the Treatment Start Date coincide, the AE onset date will be set to the Treatment Start Date
- When the Treatment Start Date is not missing, and AE Start Date is after the Treatment Start Date according to the given year or month, then the AE Start Date will be imputed as 01-MMM-YYYY

If the AE stop date is missing, then the event will be assumed to be ongoing and a stop date will not be imputed.

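### The double-blind TEAE window is not capped at the first open-label dose, and the partial-date rules ignore that dose, so some AEs that begin on open-label pirfenidone count under the randomised arm

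*SAP*

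**What the plan says.** **Double-blind window.** SAP 4.6.2 defines TEAEs as "AEs that started or worsened on or after first intake of randomized treatment until last positive dose of randomized treatment + 28 days". SAP 4.2 repeats the limit for all double-blind safety analyses, which run "until the date of last positive dose of randomized treatment plus 28 days". SAP 2.2.4 and 4.2.4 say the same. None of them mentions open-label dosing.

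**Open-label start.** Protocol 4.3.4 starts open-label pirfenidone at the Follow-up Visit, which Appendix 1 places at Day 196 with a window of ±5 days. Appendix 1 note b lets patients who left because of unblinding start on the day of a visit held 28 ±5 days after their last dose. Under Protocol 4.2 these can be placebo patients.

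**Open-label AE period.** SAP 4.2.5: "This period starts on the day of the first positive dose of pirfenidone after the 28 days follow-up visit". SAP 4.7 then counts "AEs that started or worsened on or after the date of safety follow-up period start until the end of the safety follow-up".

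**Partial onset dates.** Under SAP 4.8, "missing start dates will only be imputed for determination of whether the adverse event is considered to be treatment-emergent or not". Dates move to the earliest possible day, and the only anchors are the Treatment Start Date and the consent, screening and randomisation dates. If the day is missing and onset is after treatment start "according to the given year or month, then the AE Start Date will be imputed as 01-MMM-YYYY". For a missing month, it provides that where "the years of AE Start Date and Treatment Start Date coincide, the AE onset date will be set to the Treatment Start Date". Should the years differ, the date becomes 1 January of the stated year, unless one of the consent, screening or randomisation dates is later.

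**Same-day convention.** SAP 4.2.2, Table 1: "Adverse events occurring on the date of first randomized pirfenidone/placebo treatment will not be considered baseline, but treatment-emergent".

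**The concern.** The double-blind window and the open-label period meet on the same nominal day, and nothing closes the first when the second opens. A visit held a few days early, inside its allowed window, puts several days of open-label dosing inside the double-blind window. The partial-date rules can pull later open-label events back as well, because they never look at the first open-label dose.

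At stake are the randomised-arm AE counts: the tables by system organ class and preferred term in SAP 4.6.2, and the repeat of the rates-per-100-patient-years comparison that runs to 28 days after the last dose. The weeks just after open-label start are when pirfenidone events are expected. Protocol 5.1.1.2 puts the highest gastrointestinal incidence in the first 3 months, and Protocol 5.1.1.6 has half of the patients who reported fatigue (81/162) doing so within the first month. A former placebo patient is new to the drug at that point, and such an event could appear in the placebo column.

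**Working it through.** **Inputs from the documents.** Double-blind treatment lasts 24 weeks = 168 days; Follow-up Visit on Day 196 ±5; TEAE window to last dose + 28.

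**The plan's own figure.** 168 + 28 = 196. For a patient whose last dose is on Day 168, the scheduled open-label start is therefore the last day of the double-blind window.

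**Fully dated events.** Let g be the number of days from last randomised dose to first open-label dose. The open-label days inside the window, counting the day of the first dose, number 29 − g for g ≤ 28 and 0 for g ≥ 29. That is 6 days at g = 23, 1 at g = 28 and none later. If onset is even over the first 30 open-label days (assumption), the share in the window is (29 − g)/30.

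| Assumed spread of g | Calculation | Share of first-30-day AEs |
|---|---|---|
| even over 23 to 33 | (6+5+4+3+2+1)/(11 × 30) = 21/330 | 6.4% |
| all at 28 | 1/30 | 3.3% |
| even over 28 to 33 | 1/(6 × 30) = 1/180 | about 0.6% |

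Over a full open-label year the first row falls to 21/(11 × 365) = 0.5%.

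**Which tables such an event enters.** Every event in the overlap is in the double-blind tables. If it falls on the visit day itself, it also meets SAP 4.7 only if a visit-day dose counts as coming after the visit under SAP 4.2.5; otherwise it is in the double-blind table alone. Overlap beyond the visit day exists only when the visit is before +28.

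**Day-missing events.** The rule misplaces an event when the 1st of its month is on or before the window end, which in practice means the calendar month of open-label start. At g = 28 the whole remainder of that month is captured. With start dates even over a 365-day year and last dose on Day 168 (assumptions), the mean is Σ L(L+1)/2 over months of length L, divided by 365: (7 × 496 + 4 × 465 + 406)/365 = 5738/365 = 15.7 open-label days (range 1 to 31). Enumeration gives means of 20.7 days at g = 23 and 11.0 at g = 33. Later months are placed correctly.

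**Month-missing events.** At g = 28, every event from open-label start to 31 December is dated either to the first randomised dose or to a 1 January inside the window. The mean is (365 + 1)/2 = 183 of 365 open-label days.

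**Dated example.** First dose 25 November 2017, last dose 11 May 2018, window end and open-label start 8 June 2018.
- Onset 20 June 2018, day missing: imputed to 1 June, a double-blind TEAE.
- Onset in November 2018, month missing: imputed to 1 January 2018, a double-blind TEAE.

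The result is the same in either arm.

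**Counts, for illustration only.** The documents give no rollover rate and no open-label AE rate. Assume 50–100% of 125 patients per arm roll over, with 0.25 to 1 AE each in the first 30 open-label days. Fully dated misplacements per arm then run from 62.5 × 0.25 × 1/180 = 0.1 to 125 × 1 × 21/330 = 8.0. The upper end needs every planned patient to roll over. That is unlikely, since early discontinuers normally leave the trial (Appendix 1 note b) and entry depends on patient request and investigator judgment.

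**Effect of a cap on partial dates.** With g even over 23 to 33, simulation puts 52% of day-missing first-30-day events in the window now and 46% with a cap alone, because the imputed 1st of the month usually precedes the open-label dose. Partial dates therefore need separate handling.

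**The case against.** **A boundary at +28 days looks deliberate.** Protocol 5.3.1 collects AEs to 28 days after last dose. SAP 4.1.4 defines the follow-up population by dosing after randomised treatment end plus 28 days, and SAP 4.4.4 classes medications as post-treatment on the same cut. This stands as the reason for the 28-day limit. It does not say what happens when the second drug period opens on or before that day.

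**Earliest-date imputation is a recognised conservative rule.** It guards against losing treatment-emergent events, and a day-missing event in the month of open-label start may well have begun off drug. This stands too, and is why the fix does not reassign such events by default. The rule is not conservative for the placebo column once an active-drug period follows.

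**The period flag already separates the periods.** SAP 4.6.2 provides the flag for a listing. It lets misplaced events be traced, but there is no rule for overlap or partial dates, and the tables do not depend on it.

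**The percentages follow the assumed gap.** Correct. For completers the ±5 days applies to Day 196, not to days since last dose, and Day 168 has its own ±5. If both vary evenly and independently, the share is 286/(121 × 30) = 7.9%; if starts fall only at +28 to +33, it is about 0.6%. No single value should be quoted as the plan's error rate.

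**The consequence is small.** SAP 4.6 plans no formal safety testing. The main Phase III comparisons stop at day 168, so fully dated events after scheduled open-label start cannot enter them. AEs are elicited at every contact and open-label visits are monthly for six months, so year-only dates should be rare.

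**Conclusion.** The gap is real on the text: followed as written, the SAP can place AEs that begin on open-label pirfenidone in the randomised-arm tables of either arm. For fully dated events this needs an open-label start at or before +28 days. The share of first-30-day events is 6.4%, 3.3% or about 0.6% under the three stated spreads of start day. Partial dates reach further per event, but their number is unknown. The total cannot be derived from the documents and is probably small.

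Three stronger readings are not supported.
- A reader might infer that every overlap event is counted in both tables. On the visit day this depends on how SAP 4.2.5 is read.
- A reader might infer that placebo AE rates are inflated and the pirfenidone–placebo difference diluted. Patients from the pirfenidone arm also restart drug and gain events, and no rates are given, so no direction of bias is shown.
- A reader might infer a threat to efficacy. Only descriptive safety tables are affected.

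The partial-date results assume that Treatment Start Date in SAP 4.8, which that section does not define, means the first randomised dose. This is a point to consider, not a threat to the trial's conclusions.

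**What to change.** **(a) Cap the window.** In SAP 4.6.2, and in the matching statements in 2.2.4, 4.2 and 4.2.4, add:

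> For patients who enter the open-label period, the double-blind TEAE window ends at the earlier of last positive randomised dose + 28 days and the day before the first open-label dose.

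Align SAP 4.2.5 so that the safety follow-up period starts on the day of the first open-label dose, including the visit day. Same-day events then go to the period whose drug starts that day, as Table 1 of SAP 4.2.2 already does for the first randomised dose.

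**(b) Partial dates.** Where a partial onset date is compatible with onset both before and after the first open-label dose, keep the present rule and tabulate the event under both assignments as a sensitivity check. Reassign it to open-label only where existing records already show that it was first reported after that dose. No section says the AE eCRF holds the time of first report, so the rule should not depend on it.

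**Cost.** A few sentences and a small programming change. SAP 4.2.5 already needs the first open-label dose date, and no new data are collected. The downside is that an event that began on the visit day before dosing moves to open-label. SAP 4.5.8 says the primary analysis was run in March 2019, so re-derived double-blind tables are post hoc and should be shown beside the originals.

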4.9 VISIT WINDOWS

Visit windows for double-blind treatment period will be applied to vital signs and laboratory data and the derived visits will be used in the by-visit summarizations. If multiple observations fall within the same visit window, the observation with the nearest to midpoint value will be used in the analysis, if not stated otherwise. If subjects discontinue from the double-blind treatment period early the data will be assigned to the early discontinuation visit. The date of early discontinuation will be considered as the target date.

The "Baseline" visit is a derived data point to identify baseline values which are used to calculate the change from baseline values. Baseline is defined in Section 4.2.2.

The End of Treatment [EOT] visit will either be a copy of early discontinuation records for patients who prematurely discontinued double-blind treatment period or Week 24 records for patients who completed the double-blind treatment period.

Table 2 Visit Windows

| Analysis Visit [AVISITN] | Target Day | Analysis Window (scheduled Study Days) |
|--------------------------|------------|--|
| Baseline [0] | 1 | Last valid assessment prior to first intake of randomized study drug (pirfenidone/placebo). |
| | | Generally, it is assumed that measurements referring to the Day 1 (Week 1) visit have been performed before randomized study drug (pirfenidone/placebo) was given. |
| Week 4 [4] | 28 | One day after first dose of randomized treatment to 42 |
| Week 8 [8] | 56 | 43 to 70 |
| Week 12 [12] | 84 | 71 to 98 |
| Week 16 [16] | 112 | 99 to 126 |
| Week 20 [20] | 140 | 127 to 154 |
| Week 24 [24] | 168 | 155 to a maximum of 195 if the patient did not early discontinued. |

Pirfenidone — F. Hoffmann-La Roche Ltd

| Early discontinuation [25] | Not applicable | As occurred |
|--|----------------|---|
| End of treatment (EOT) [26] | Not applicable | As occurred |
| Follow-up visit (FUP1) [27] | Not applicable | As occurred |
| Safety follow-up visits(SFUP) [28] | Not applicable | As occurred: Month 1 to 6: Monthly visits Month 7 to 12: Approximately every 3 months |
| Additional Safety follow-up visit [29] | Not applicable | As occurred: up to 12 months plus 28 days |

